13.5 Analysis of Exploratory Endpoints

Genomic signatures that may predict responses to Pembrolizumab and radiation will be explored using logistic regression. Descriptive statistics such as mean, standard deviation, median and range, will be reported for the levels of circulation tumor DNA and immunologic correlates. Comparison between different time points can be made by t-test or Wilcoxon test where appropriate. Logistic regression will be carried out to examine their association with response to pembrolizumab and SBRT.

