9.1.1.2 RNAseq of Tumor

Whole transcriptome sequencing of tumor RNA will be performed using next generation sequencing in OICR with established protocols (see Lab Manual). RNAseq data will be used to perform exploratory analysis. Planned analyses include evaluation of differences in gene expression levels between responders and non-responders to study treatment. Further exploratory analyses will include interrogation of inflammatory signatures. In patients consenting for a second optional biopsy, immune signatures will be compared pre and post treatment.

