Target lesions. All measurable lesions up to a maximum of 2 lesions per organ and 5 lesions in total, representative of all involved organs, should be identified as **target lesions** and recorded and measured at baseline. Target lesions should be selected on the basis of their size (lesions with the longest diameter), be representative of all involved organs, but in addition should be those that lend themselves to reproducible repeated measurements. Vascular thrombi will not be selected as target lesions, unless vascular HCC is the only HCC present. It may be the case that, on occasion, the largest lesion does not lend itself to reproducible measurement in which circumstance the next largest lesion which can be measured reproducibly should be selected. A sum of the diameters (longest for non-nodal lesions, short axis for nodal lesions) for all target lesions will be calculated and reported as the baseline sum diameters. If lymph nodes are to be included in the sum, then only the short axis is added into the sum. The baseline sum diameters will be used as reference to further characterize any objective tumor regression in the

measurable dimension of the disease. Radiated lesions can be counted as target lesions provided there has been demonstrated progression in the lesion.

Non-target lesions. All other lesions (or sites of disease) including any measurable lesions over and above the 5 target lesions should be identified as **non-target lesions** and should also be recorded at baseline. Measurements of these lesions are not required, but the presence, absence, or in rare cases unequivocal progression of each should be noted throughout follow-up.

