11.1.4 RECIST/ iRECIST Assessment of Disease

Response

All patients will have their BEST RESPONSE from the start of study treatment until the end of treatment classified as outlined below:

Complete Response (CR): disappearance of *target* and *non-target* lesions and normalization of tumour markers. Pathological lymph nodes must have short axis reduction to < 10mm (Note: continue to record the measurement even if < 10mm and considered CR). Residual lesions (other than nodes < 10mm) thought to be non-malignant should be further investigated (by cytology specialized imaging or other techniques as appropriate for individual cases [ref RECIST 1.1]) before CR can be accepted. Confirmation of response is required

Partial Response (PR): at least a 30% decrease in the sum of measures (longest diameter for tumour lesions and short axis measure for nodes) of target lesions, taking as reference the baseline sum of diameters. Non target lesions must be non-PD. Patients with CR/iCR or PR/iPR should have scans repeated after 4 weeks, but no more than 8 weeks, to confirm response.

Stable Disease (SD): Neither sufficient shrinkage to qualify for PR nor sufficient increase to qualify for PD taking as reference the smallest sum of diameters on study

Progressive Disease (PD): at least a 20% increase in the sum of diameters of measured lesions taking as references the smallest sum of diameters recorded on study (including baseline) AND an absolute increase of $\geq 5\text{mm}$. Appearance of new lesions will also constitute progressive disease (including lesions in previously unassessed areas). When the patient has only non-measurable disease, unequivocal progression of non-target disease may be accepted as evidence of disease progression, where the overall tumour burden has increased sufficiently to merit discontinuation of treatment or where the tumour burden appears to have increased by at least 73% in volume. Modest increases in the size of one or more non-target lesions are NOT considered unequivocal progression. If the evidence of PD is equivocal (target or non-target), treatment may continue until the next assessment, but if confirmed, the earlier date must be used.

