13.2 Sample Size/Accrual Rate

Given the preliminary results with nivolumab, we would expect that pembrolizumab alone would produce responses in 15% of patients.²⁴ We hypothesize that combining pembrolizumab with SBRT will increase the ORR to 40%, a clinically meaningful increase in systemic response rate and indicative of significant activity (Note: ORR is a composite sum of irradiated local tumor and other measurable metastatic disease - local radiotherapy response, systemic pembrolizumab response and potential abscopal effect on all measurable disease).

With 90% power, we would need to accrue 22 evaluable patients in a two-stage study design, with a one-sided significance level of 10%. If 2 or more patients show response from the first 10 evaluable patients, we will continue to accrue to a total of 22 evaluable patients. We expect to accrue up to 27 patients as some patients may not be evaluable for the primary endpoint. A total number of 6 or more responders in 22 evaluable patients would be considered to reject the null hypothesis. We expect to accrue 2-3 patients per month, leading to complete accrual in 12 months following study activation.

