13.3 Analysis of Primary Endpoint

Overall Response Rate (ORR)

ORR is defined as the proportion of the subjects in the study population who have a complete response (iCR) or partial response (iPR), as defined by iRECIST, at any time on study treatment. This is noting that radiated lesions will count as target lesions provided there has been demonstrated progression in the lesion.

The point estimate and 95% confidence interval for ORR will be provided using the Clopper and Pearson exact binomial method. An interim analysis for futility will be undertaken when response data are available on the first 10 evaluable subjects enrolled. If ≤ 1 responses are documented, the trial will be stopped. If 2 or more responses (iCR or iPR) are documented, the study will continue to full accrual. Subjects who are inevaluable for the primary endpoint will be replaced.

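### Section 13.5 relates biomarkers only to yes/no response; adding percent change in target-lesion size as a further exploratory outcome would recover power at no data cost

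*Combined protocol and SAP*

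**What the plan says.** Section 13.5 gives the same model for each group of markers. For tumour genomics: "Genomic signatures that may predict responses to Pembrolizumab and radiation will be explored using logistic regression". For ctDNA and the immunologic correlates: "Logistic regression will be carried out to examine their association with response to pembrolizumab and SBRT". The t-test and Wilcoxon test in that section compare time points and do not relate a marker to an outcome. Section 9.1.1.2 also works from the response category: "Planned analyses include evaluation of differences in gene expression levels between responders and non-responders to study treatment".

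The response category is built partly on a continuous measure. Under Section 11.1.2 a sum of diameters "for all target lesions will be calculated and reported as the baseline sum diameters", and "The baseline sum diameters will be used as reference to further characterize any objective tumor regression". Section 11.1.4 defines partial response in the target lesions as "at least a 30% decrease in the sum of measures". The Study Calendar schedules tumour measurements at 12 weeks and repeatedly thereafter. No section analyses percent change in the sum.

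Section 9 labels the biomarker work exploratory. The plan gives no alpha, effect size or power for it.

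**The concern.** Several of the markers in Section 1.3 are continuous, such as ctDNA level, PD-L1 percentage and cytokine levels. Cutting the outcome at a 30% decrease treats a tumour that shrank by 29% like one that grew by 15%, and treats a 31% decrease like a 90% decrease. At 22 evaluable subjects there is little information to spare. The 40% response rate that the design hopes for yields about 9 responders (22 × 0.40 = 8.8), and the null rate of 15% yields about 3 (22 × 0.15 = 3.3).

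What is at stake is the return on the mandatory pre-treatment biopsy and the serial blood samples. The fewer the responders, the less the stated analysis can say about them, and few responders is an outcome the design explicitly allows for.

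**Working it through.** **1. The plan's own figures.** Section 13.2 gives p0 = 0.15, p1 = 0.40, 22 evaluable subjects and rejection at 6 or more responders. Section 13.3 stops the trial at 1 or fewer responders among the first 10. The exact calculation sums, over stage-1 counts x ≥ 2, P(X1 = x) × P(at least max(0, 6 − x) responders among the next 12).
- At p = 0.15 the rejection probability is 0.0907, within the stated 10%.
- At p = 0.40 it is 0.903, matching the stated 90%.

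The design figures reproduce and are not in question. No power figure is stated for the biomarker analyses, so there is none to reproduce.

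**2. Power for one marker.** From the plan: n = 22 and response rates of 15% and 40%, with 25% added as an intermediate value. Assumed here: two-sided 5% level; marker and percent change bivariate normal with correlation ρ; response defined as percent change beyond the cut that gives the stated response rate; every subject has a percent change; no new-lesion or non-target progression. The logistic likelihood-ratio test is size-corrected, because uncorrected its type I error is about 6 to 7%. There were 20,000 simulated trials per cell.

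| ρ | Response rate | Spearman on percent change | Logistic, size-corrected | Difference (points) |
|---|---|---|---|---|
| 0.3 | 15% | 0.251 | 0.131 | 12 |
| 0.3 | 25% | 0.248 | 0.154 | 9 |
| 0.3 | 40% | 0.249 | 0.195 | 5 |
| 0.4 | 15% | 0.411 | 0.203 | 21 |
| 0.4 | 25% | 0.418 | 0.257 | 16 |
| 0.4 | 40% | 0.410 | 0.308 | 10 |
| 0.5 | 15% | 0.621 | 0.299 | 32 |
| 0.5 | 25% | 0.624 | 0.388 | 24 |
| 0.5 | 40% | 0.618 | 0.467 | 15 |
| 0.6 | 15% | 0.812 | 0.436 | 38 |
| 0.6 | 25% | 0.821 | 0.557 | 26 |
| 0.6 | 40% | 0.815 | 0.653 | 16 |

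A separate run at ρ = 0.5 gave Spearman 0.60 to 0.62 against logistic 0.29, 0.41 and 0.46, agreeing to about 2 points.

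**3. Some subjects without a percent change.** If 4 of the 22 have none, linear regression on the other 18 at ρ = 0.5 has power 0.590, 0.594 and 0.585 at response rates of 15%, 25% and 40%. The advantage over size-corrected logistic regression on all 22 is then 29, 21 and 12 points.

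**4. After a futility stop.** At a true rate of 15%, P(0 or 1 responders of 10) = 0.85^10 + 10 × 0.15 × 0.85^9 = 0.197 + 0.347 = 0.544. With 0 responders the logistic model cannot be fitted; with 1 it carries almost no information. Percent change would still give a descriptive analysis of the ten subjects' markers.

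**5. Progression outside the target lesions.** Give the worst rank to subjects with new-lesion progression, hold ρ at 0.5 and the response rate at 40%, and let 20%, 30% or 40% of subjects progress this way (assumed shares). If the marker predicts new lesions as strongly as it predicts shrinkage, the worst-rank analysis beats logistic regression by 15, 10 and 5 points. If it does not predict new lesions, it is worse by 3, 5 and 4 points. Across other settings with 20 to 35% new-lesion progression, the difference ran from about −11 to +36 points.

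**The case against.** The objectives ask for predictors of response, and logistic regression answers that directly. The work is declared exploratory, no single marker is pre-chosen, and a one-marker test at 5% does not describe a genome-wide screen. Percent change is also an imperfect outcome here. It includes irradiated lesions, which Section 11.1 warns are hard to assess; it ignores new lesions, although Section 2.2.2 says progression outside the irradiated volume is common after SBRT alone; and vascular-only disease is judged by qualitative thrombosis rules. Section 13.4 already allows Cox models of unnamed factors for DOR, PFS and OS.

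Most of this stands, and it limits the point to an addition. It does not remove the gap: no named analysis uses the size measure, and the Cox models name no biomarker.

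A reader might infer three stronger conclusions that the documents do not support.
- **A loss of 20 to 35 points, or more, as a general figure.** That size comes from setting Pearson correlation against a logistic Wald test. Section 13.5 does not name the Wald test, whose type I error here is only about 1 to 2%. At the design's 40% response rate, no size-corrected loss exceeds about 22 points, even with linear regression on complete data.
- **That percent change should replace response as the main biomarker outcome.** Step 5 shows that the worst-rank version can lose to logistic regression.
- **That the plan discards the measurements.** The diameters stay recorded, and percent change can be derived at any time.

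**Conclusion.** The point holds as a low-severity gap in the exploratory analysis. Section 13.5 uses binary response as the only outcome for biomarkers, while a fuller measure is already collected. For a single continuous marker at n = 22, ρ = 0.5, complete data and size-corrected tests, the loss is roughly 15 points at a 40% response rate and roughly 30 at 15%. At ρ = 0.3 it is 5 to 12 points.

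The correlation, the 5% level and the normal model are assumptions; the documents give none of them. The model also leaves out progression outside the target lesions, which can remove or reverse the advantage once it is ranked worst. The case is firmest when responders are few, because there logistic regression is nearly or wholly uninformative. The primary endpoint, its decision rule and its operating characteristics are unaffected.

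**What to change.** Add to Section 13.5 that, for pre-chosen continuous markers, best percent change from baseline in the sum of target-lesion diameters will also be analysed, by Spearman correlation or linear regression, as an additional exploratory outcome. Keep logistic regression on iCR/iPR.

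Report the target-lesion analysis itself. Beside it, report a sensitivity analysis that gives the worst rank to subjects with new-lesion or non-target progression and to those with early progression or death without a scan. State how subjects with vascular-only disease are handled, since they have no standard sum. Fix the wording before marker results are seen, so that the outcome scale is not chosen afterwards.

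The cost is a few sentences and a little analysis time, with no new data or visits. The downsides are that percent change covers target lesions only, irradiated ones included; that the result is a correlation or slope and not an odds ratio for response; and that the worst-rank version can have less power than logistic regression if the marker does not predict new lesions.

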13.6 Reporting and Exclusions

13.6.1 Evaluation of Toxicity

All subjects will be evaluable for toxicity from the time of their first treatment with pembrolizumab. Toxicities will be evaluated and graded according to CTCAE v4.0, and will be assigned an attribution as per Section 7.2. Safety and tolerability will be assessed by clinical review of all relevant parameters including AEs, laboratory tests and vital signs.

Toxicity tables will be constructed to summarize the observed incidence of adverse events by toxicity and grade. The relative frequency of each type of toxicity will be quantified as the number of toxicity-evaluable cycles in which the adverse event was noted as grade 3 or higher considered by the treating physician to be possibly, probably or definitely related to one of the agents in the regimen, divided by the number of toxicity-evaluable cycles administered to patients enrolled on the trial.

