5. TREATMENT PLAN

5.1 Agent Administration

Treatment will be administered on an outpatient basis. Appropriate dose delays and management of adverse events are described in Section 6. No investigational or commercial agents or therapies other than those described below may be administered with the intent to treat the subject's malignancy.

Regimen Description			
Agent	Dose	Route	Schedule
Pembrolizumab	200 mg	IV over 30 minutes	Every 3 weeks
SBRT administered to dominant hepatic HCC			Starting day 2 of cycle 1 pembrolizumab, given in 5 fractions over 5-15 days

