6.2 Guidance for Diagnosis and Management of Hepatic Events of Clinical Interest (ECIs)

In addition to overdose, hepatic ECIs will include any of the following events. All of these events will require holding pembrolizumab treatment and notification of the Sponsor within 24 hours. Refer to Section 7 for reporting guidelines.

All cases of retreatment and permanent discontinuation must be reported to the Sponsor and recorded in the database.

a) ALT:

- i) Among subjects with baseline ALT $<2 \times \text{ULN}$: ALT $\geq 5 \times \text{ULN}$
- ii) Among subjects with baseline ALT $\geq 2 \times \text{ULN}$: ALT $> 3 \times$ the baseline level
- iii) ALT $> 500 \text{ U/L}$ regardless of baseline level

(Subjects with ALT $> 5 \times \text{ULN}$ at baseline are not eligible for enrollment)

b) AST:

- i) Among subjects with baseline AST $<2 \times \text{ULN}$: AST $\geq 5 \times \text{ULN}$
- ii) Among subjects with baseline AST $\geq 2 \times \text{ULN}$: AST $> 3 \times$ the baseline level
- iii) AST $> 500 \text{ U/L}$ regardless of baseline level

(Subjects with AST $> 5 \times \text{ULN}$ at baseline are not eligible for enrollment)

c) Total Bilirubin:

- i) Among subjects with baseline levels $< 22 \text{ umol/L}$: a value of $> 34 \text{ umol/L}$
- ii) Among subjects with baseline levels that are $\geq 22 \text{ umol/L}$: a value $\geq 2 \times$ the baseline level
- iii) Total bilirubin $> 51 \text{ umol/L}$ regardless of baseline level

(Subjects with total bilirubin $> 34 \text{ umol/L}$ at baseline are not eligible for enrollment)

d) Regardless of laboratory values, hepatic decompensation diagnosed clinically, including:

- i) New onset clinically detectable ascites
- ii) Gastrointestinal bleeding suggestive of portal hypertension (e.g., esophageal or gastric varices)
- iii) Encephalopathy

(Subjects with clinically apparent ascites or encephalopathy, or untreated varices at baseline are not eligible for enrollment)

Immediate assessment

All subjects

- All subjects should be evaluated according to directions below within 72 hours of alert for non-overdose ECI
- Procedures:
 - Obtain an opinion from a hepatologist
 - Obtain a work-up for hepatitis if there is no underlying hepatitis, including hepatitis A, B, C, D, Epstein-Barr virus serology, and cytomegalovirus serology

- Assess for ingestion of drugs/supplements with hepatotoxic potential
- Assess for alcohol ingestion

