7.1.1.2 Expected Adverse Events for SBRT

Very likely (80-90%)

- Fatigue (which generally resolves after radiation therapy is completed)
- Skin irritation, redness, itchiness, discomfort
- Temporary changes in blood work, without symptoms

Less likely (30%)

- Nausea, vomiting (during therapy) – more common if stomach or GI tract irradiated
- Diarrhea or sensitivity to food – more common if GI tract irradiated
- Gastritis, esophagitis, duodenitis, colitis – more common if relevant portion of the GI tract is irradiated
- Gastric, esophagus, small bowel or large bowel irritation/ulceration, bleeding, fistula, obstruction or changes in motility following therapy (may require medications or surgery) (<10% permanent changes)
- Chest wall pain, rib fracture (< 10%)

Less likely, but serious (<1-25%)

- Radiation-induced liver disease (RILD) (<5%). Classic RILD is a clinical diagnosis of anicteric ascites, hepatomegaly and elevation of ALP relative to other transaminases that may occur 2 weeks to 3 months following radiation to the liver.
- Non-classic RILD includes elevation of liver enzymes and/or any decline in liver function within 12 weeks from start of therapy (~25%). RILD can lead to liver failure that could lead to death. There is an increased risk of liver toxicity in patients with large tumors and in patients with pre-existing liver disease.
- Permanent thrombocytopenia (<1%); this may lead to bleeding
- Kidney injury (<1%); this may lead to changes on imaging and more rarely the need for medication.

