10. STUDY CALENDAR

Baseline (pre-study) evaluations are to be conducted within 14 days prior to start of protocol therapy, unless specified differently in the study calendar. Scans (including tumor measurements) x-rays, informed consent, tumor biopsy, and hepatitis testing must be done \leq 28 days prior to the start of therapy. In the event that the subject's condition is deteriorating, laboratory evaluations should be repeated within 48 hours prior to initiation of the next cycle of therapy. Some visits might be conducted remotely and / or some assessments might be deferred as per physician discretion. Some of the safety lab assessments may also be done at external or community laboratories as applicable. In such cases, sites should provide Normal reference ranges of such lab and lab licenses to the Central Office.

The following schedule of assessments applies to all subjects. More frequent assessments should be obtained if clinically indicated. If pre-study laboratory and clinical assessments were done within 5 days prior to treatment initiation, they do not need to be repeated for cycle 1 day 1. For subsequent cycles 2+, day 1 assessments can be completed up to 4 days prior to day 1. A cycle is 21 days long for the purposes of this protocol.

		Cycle 1				Cycle 2	Cycle 3	Cycle 4	Cycle 5	Cycle 6+	Off Treatment Visit ^c	Survival Follow-Up ^c
		Pre-Study	Day 1	Day 2	Day 5	Day 10	Day 1	Day 1	Day 1	Day 1		
Pembrolizumab		A					A	A	A	A		
SBRT			B-----B									
Informed consent (Main and Optional)	X											
Demographics	X											
Medical history	X											
TNM Staging, BCLC Staging	X											
Vascular Thrombosis Staging ^f	X											
Concurrent meds	X	X-----X										
Physical exam	X	X		X ^e		X	X	X	X	X		
Vital signs ^d	X	X	X	X ^e		X	X	X	X	X		
Height	X											
Weight	X	X				X	X	X	X	X		
Performance status	X	X	X			X	X	X	X	X		
Child-Pugh Score	X	X		X ^e		X	X	X	X	X		
ALBI Score	X	X		X		X	X	X	X	X		
CBC w/diff, PT/INR	X	X		X ^e		X	X	X	X	X		
Neutrophil-Lymphocyte Ratio	X	X		X		X	X	X	X	X		
Serum chemistry ^a	X	X		X ^e		X	X	X	X	X		
T3 and TSH	X	X					X		X			
Hepatitis B Testing ^g	X											
Hepatitis C Testing ^h	X											

Anti-HDV Testing ^j	X										
ECHO	X										
EKG	X										
Adverse event evaluation				X-----			X		X		
Tumor measurements	X				X ^m					X ⁱ	
					Documentation (radiologic) must be provided for subjects removed from treatment for progressive disease.						
Radiologic evaluation	X					X ^m				X ⁱ	
B-HCG	X ^b										

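### Section 13.6.1 defines related grade 3 or higher toxicity only as a per-cycle ratio, which does not estimate a patient's risk from SBRT plus pembrolizumab; the incidence tables beside it state no denominator

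*Combined protocol and SAP*

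**What the plan says.** Section 13.6.1 makes three statements about toxicity summaries.

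- Population: "All subjects will be evaluable for toxicity from the time of their first treatment with pembrolizumab".
- Tables: "Toxicity tables will be constructed to summarize the observed incidence of adverse events by toxicity and grade". The sentence gives no denominator, no relatedness filter, no worst-grade rule and no confidence interval.
- Rate: "The relative frequency of each type of toxicity will be quantified as the number of toxicity-evaluable cycles in which the adverse event was noted" at grade 3 or higher and judged at least possibly related to an agent in the regimen, "divided by the number of toxicity-evaluable cycles administered to patients enrolled on the trial".

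The rate is defined separately for each type of toxicity. No overall proportion of patients with any related grade 3 or higher event is defined. Subjects are defined as evaluable for toxicity (11.1.1 and 13.6.1), but an evaluable cycle is not defined anywhere.

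Other sections set the context:

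- Section 10: "A cycle is 21 days long for the purposes of this protocol".
- Section 5.1, on SBRT: "Starting day 2 of cycle 1 pembrolizumab, given in 5 fractions over 5-15 days".
- Section 5.3 lets pembrolizumab run to 24 months or 35 administrations, whichever is later.
- Section 1.2, objective 5, is the safety and tolerability of the combination in subjects.
- Section 7.1.1.2 describes classic radiation-induced liver disease (RILD) as an event "that may occur 2 weeks to 3 months following radiation to the liver". It places non-classic RILD within 12 weeks from the start of therapy.

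**The concern.** The objective asks what happens to patients who receive one SBRT course with pembrolizumab. A ratio of cycles answers a different question. Its denominator grows with every later pembrolizumab cycle, most of which contain no SBRT, so the same number of harmed patients gives a smaller figure when the others stay on drug longer. It also mixes the number of patients affected with the number of cycles each event lasts.

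The result cannot be set beside the toxicity figures the protocol uses itself, which count patients. Section 2.2.3 cites grade 3 toxicity in 12 of 35 patients (34%) in one ipilimumab and SBRT study, and grade 3/4 toxicity in 14% of patients in another. Section 2.2.2 cites a Child-Pugh decline in about 30% of patients. The first-10 liver rule in 5.1.2.1 counts patients too. Section 2.2.3 says prospective toxicity data are needed, particularly in HCC, so a usable figure matters here.

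The second problem is the undefined term. If only administered 21-day cycles can hold an event, a liver event that appears after an early stopper's last cycle may have nowhere to be counted.

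**Working it through.** **The plan's own figures.** Section 13.6.1 gives no numerical toxicity figure to reproduce. The only design figures are for response (13.2): continue if at least 2 of 10 respond, then declare success at 6 or more of 22. Exact binomial calculation gives type I error 0.091 at 15% and power 0.903 at 40%. This agrees with the stated 10% one-sided level and 90% power, and toxicity reporting does not touch it.

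**Inputs.** Patient numbers: the 10 patients and the count of 3 come from the liver rule in 5.1.2.1; 22 evaluable and up to 27 accrued come from 13.2. Cycle counts are assumed, because the documents give none: each affected patient has 2 cycles, 1 of them affected, and each unaffected patient has k = 4, 6, 10 or 16.

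**Formulas**, for one toxicity type, with x affected patients among n treated:

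- Per patient = x / n, with a Clopper-Pearson 95% interval.
- Per cycle, as in 13.6.1 = x / (2x + (n − x)k).

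**Results**

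| x of n | Per patient (95% CI) | k = 4 | k = 6 | k = 10 | k = 16 |
|---|---|---|---|---|---|
| 3 of 10 | 30.0% (6.7 to 65.2) | 3/34 = 8.8% | 3/48 = 6.3% | 3/76 = 3.9% | 3/118 = 2.5% |
| 3 of 22 | 13.6% (2.9 to 34.9) | 3/82 = 3.7% | 3/120 = 2.5% | 3/196 = 1.5% | 3/310 = 1.0% |
| 3 of 27 | 11.1% (2.4 to 29.2) | 3/102 = 2.9% | 3/150 = 2.0% | 3/246 = 1.2% | 3/390 = 0.8% |

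**Sensitivity for 3 of 10.**

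- Affected patients with 1 cycle each: 3/31 = 9.7% down to 3/115 = 2.6%.
- Affected patients with 4 cycles each: 3/40 = 7.5% down to 3/124 = 2.4%.
- Each event spanning both of 2 cycles: the figures double, 6/34 = 17.6% down to 6/118 = 5.1%.

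The dependence on time on drug remains in every case.

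**The ratio cannot be turned back into patients.** Suppose 22 patients have 6 cycles each, 132 in all, and 4 cycles are affected. The rate is 4/132 = 3.0% whether one patient had an event lasting four cycles (1/22 = 4.5%) or four patients had one each (4/22 = 18.2%).

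**Timing.** With 21-day cycles, the last administered cycle ends on day 21, 42, 63 or 84 after 1, 2, 3 or 4 doses.

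- SBRT starts on day 2 and takes 5 to 15 days, so it ends on day 6 to 16. Taking 3 months as 91 days, the classic RILD period runs from day 20 to 30 (plus 14) until day 97 to 107 (plus 91).
- The 12-week period for non-classic RILD, counted from day 1, ends on day 84.

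Both periods outlast the last administered cycle after 1 to 3 doses. After 4 doses only the classic period does. The plan does not say how an event in that gap is assigned.

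**The case against.** The strongest reply is that 13.6.1 does not rely on the ratio alone. The incidence tables follow directly from a subject-level toxicity population and are probably meant per subject. Attribution is recorded for each event, so a per-patient table can be derived from data already collected. Safety is to be judged by clinical review, a DSMB reviews data throughout (7.9), and the one numerical safety rule (5.1.2.1) already counts patients. The cycle counts above are assumptions. All of this stands, and it limits the point to how safety is summarised. It does not supply the missing denominator, relatedness filter, overall proportion or interval.

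Several stronger readings are tempting and not supported:

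- *Harmed patients systematically leave the denominator.* Section 6.2 says of hepatic events of clinical interest: "All of these events will require holding pembrolizumab treatment". But holding is not stopping. Sections 6.1 and 6.2 allow resumption in many cases, and such an event is not the same as a related grade 3 or higher event.
- *A stated share of liver events will be lost.* The periods above are calendar days. The documents give no event-time distribution and no early-stopping rate.
- *Section 5.1.2.1 already fixes a 3-month window for all grade 3 or higher hepatic toxicity.* The phrase follows the grade 4/5 clause and may apply only to that.
- *Sections 7.2 and 7.6 conflict over late events.* The first covers SAE reporting after discontinuation and the second covers AE follow-up after the Off Treatment Visit. These are different duties.

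**Conclusion.** The point holds as a weakness in the safety summary. The only defined rate of related grade 3 or higher toxicity measures affected cycles, varies with time on drug, and does not estimate a patient's risk from the combination. In the illustration, a 30.0% per-patient proportion reads as 8.8% to 2.5%. The size rests on assumed cycle counts, but the direction needs only that most patients have several cycles and few affected ones. The ratio usually reads lower than the per-patient proportion, not always, because an event lasting many cycles pushes it up. Whether liver events after an early stopper's last cycle are counted is left open by an undefined term.

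A reader might infer that no patient-level toxicity will be reported, or that safety decisions are compromised. The documents support neither: the incidence tables are probably per subject, and no decision rule uses the ratio. The response test and sample size are untouched. The change is worth making because it is cheap and serves a stated secondary objective.

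**What to change.** In 13.6.1:

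1. Make the main summary the number and proportion of treated patients with at least one related grade 3 or higher event, overall and by toxicity type (worst grade per patient), with exact 95% intervals. Clopper-Pearson is already named for response in 13.3 and 13.4.
2. State treated patients as the denominator of the incidence tables, and show the tables for all events and for related events.
3. Add the per-patient proportion with grade 3 or higher hepatic toxicity in a fixed reporting window of about 3 months after the initial SBRT course, counted whether or not a cycle is in progress. Naming the initial course matters because 5.3.2 permits further SBRT.
4. Keep the per-cycle rate only as a supplement. Define an evaluable cycle and say how events after the last administered cycle are assigned.

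The cost is wording and one table, almost entirely from data already collected. Reported percentages will usually be higher than the per-cycle rate, and with 22 to 27 patients the intervals will be wide.
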